Objectives	The primary objective of this study is to show that, when used before, during, and after an EP procedure, CoVa™ 2 is able to successfully measure vital signs, waveforms, and hemodynamic parameters from patients, indicate the efficacy of the EP procedure, and show any signs of patient decompensation or complications. An additional objective of this study is to show that, through use of CoVa™ 2, patients can be discharged relatively early from the hospital after undergoing an EP procedure.
Methodology	No randomization or blinding methods will be used for this study.
Endpoint	The primary endpoint will be if at least 50% of subjects studied in this trial are able to be discharged relatively early from the hospital if they are monitored with CoVa™ 2. A detailed retrospective statistical report will be the determining factor in meeting this success criteria.
Study Duration	Approximately 6 months
Participant Duration	Up to 7 days (until hospital discharge).
Duration of IP administration	N/A
Population	Approximate sample size: 20 subjects. Subjects are those which need an EP procedure,, including atrial fibrillation and SVT, pacemaker or ICD implant.
Study Sites	NYU Medical Center Electrophysiology [name]
Number of participants	20 subjects across one site

Description of Study Agent/Procedure	Subjects will be measured with CoVa™ 2 before and after an EP procedure.
Reference Therapy	N/A
Key Procedures	EP
Statistical Analysis	Statistical comparison (e.g. correlations) of measurements made before, during, and after the EP procedure to prove or disprove the above-mentioned study hypothesis.

Schematic of Study Design

1 Key Roles

Principle Investigator
[name]
[contact]

Sub Investigator
[name]
[contact]

Introduction, Background Information and Scientific Rationale

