Once the EP procedure is complete, the subject will be transferred from the operating room to a hospital room, where they will stay overnight. Measurements will be made during this period, but not while the subject is being transferred. Once the subject is situated in the hospital room, the CoVa™ 2 Sensor will be applied to the subject and connected to the external power supply in the same manner as described above. Then measurements will commence according to the same duty cycle as described above.

The patient will continuously wear the CoVa™ 2 system until they are discharged for a period of about 24 hours. During this period, data from the sensor will be sent to the Gateway and Cloud-based System, and then analyzed retrospectively.

During the course of the study, scientists at toSense will use the Data Analytics Software to process measurement information from CoVa™ 2, with a focus of proving or disproving the study's primary hypothesis, i.e. when the CoVa™ 2 Sensor is used before, during, and after an EP procedure, can it successfully measure patients, indicate the efficacy of the EP procedure, show any signs of patient decompensation or complications, and allow a patient to be discharged relatively early?

More detailed analyses will investigate the study's secondary objectives, i.e.: 1) can measurements made by the CoVa™ 2 Sensor be successfully made before, during, and after an EP procedure; 2) is there correlation between parameters such as volume status, heart rate and arrhythmia, SV, and CO before, during, and after an EP procedure; 3) does RF ablation during an EP procedure interfere with CoVa™ 2 Sensor measurements?; 4) does a shock during a DC cardioversion interfere with CoVa™ 2 Sensor measurements?; and 5) is the usability of the CoVa™ 2 Sensor adequate before, during, and after an EP procedure suitable for clinicians?

Upon completion of the study, a report will be drafted describing the above-described information. The report may evolve into a peer-reviewed publication if this is determined by the PI to be an appropriate course of action.

This measurement protocol will be performed for a period of at approximately 6 months.

Study Endpoints

Primary Study Endpoints

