The primary endpoint will be if at least 50% of subjects studied in this trial are able to be discharged relatively early from the hospital if they are monitored with CoVa™ 2, as determined through a retrospective analysis. A detailed retrospective statistical report will be the determining factor in meeting this success criteria.

Study Enrollment and Withdrawal

Inclusion Criteria

In order to be eligible to participate in this study, an individual must meet all of the following criteria:

1. Patients with arrhythmias and other cardiac conditions that are scheduled for EP procedures.
2. Subject is over 22 years of age at the time of consenting
3. Subject and/or legally authorized representative is willing to undergo the informed consent process prior to enrollment in the study

Exclusion Criteria

An individual who meets any of the following criteria will be excluded from participation in this study:

1. Pregnant subjects
2. Subjects who are participating in another clinical study that may affect the results of either study

3. Subjects who are unwilling or unable to wear the sensor (and electrodes) for a period of up to 14 hours
4. Subjects who are considered by the principle investigator to be medically unsuitable for study participation

Vulnerable Subjects

Vulnerable subjects will not be utilized in this study. In the case of a vulnerable population patient being identified; they will not be included in the study or analysis..

Strategies for Recruitment and Retention

No NYULMC media will be used to recruit subjects. Subjects that are scheduled for an EP procedure and meet the inclusion criteria will be approached for enrollment.

Subjects will be consented in a quiet and private environment. Subjects will be given the opportunity to take the written consent form home to review overnight.

Use of DataCore/Epic Information for Recruitment Purposes

This study will utilize EPIC to identify subjects. Once potential subjects have been identified, the study team will notify the treating physician (TP) that they have patients eligible to participate. The study team will obtain approval from the treating physician to approach the eligible patient for the study.

Duration of Study Participation

The total duration of study participation is about 1.5 days. This includes:

Written Informed Consent Process: 1 day

Study Procedure: 1 day

Measurement prior to EP Procedure: 1-3 hours

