Measurement after EP procedure: Patient will be measured until they are discharged from hospital (approximately 24 hours).

Subjects may be contacted for a follow-up interview.

Total Number of Participants and Sites

This is a single-site study. Recruitment will end when approximately 20 participants are enrolled. It is expected that approximately 20-30 participants will be recruited in order to produce 20 evaluable participants.

Reasons for Withdrawal or Termination

Participants are free to withdraw from participation in the study at any time upon request. An investigator may terminate participation in the study if:

- Any clinical adverse event (AE), laboratory abnormality, or other medical condition or situation occurs such that continued participation in the study would not be in the best interest of the participant
- The participant meets an exclusion criterion (either newly developed or not previously recognized) that precludes further study participation

Handling of Participant Withdrawals or Termination

Withdraw criteria:

- The Principle Investigator will review whether a withdrawal of a subject affects the success criteria of the study. A subject may be replaced if it is determined that more subjects are needed based on this criterion

Premature Termination or Suspension of Study

This study may be temporarily suspended or prematurely terminated if there is sufficient reasonable cause. Written notification, documenting the reason for study suspension or termination. If the study is prematurely terminated or suspended, the PI will promptly inform the IRB and will provide the reason(s) for the termination or suspension.

Circumstances that may warrant termination or suspension include, but are not limited to:

- Determination of unexpected, significant, or unacceptable risk to participants
- Demonstration of efficacy that would warrant stopping
- Insufficient compliance to protocol requirements
- Data that are not sufficiently complete and/or evaluable
- Determination of futility

Study may resume once concerns about safety, protocol compliance, data quality are addressed and satisfy the IRB.

Study Agent (Study drug, device, biologic, vaccine etc.) and/or Procedural Intervention

Study Agent(s) and Control Description

Acquisition

toSense will ship CoVa™ 2 systems directly to the Electrophysiology supplies team at the NYU medical center.

New York Medical Center
[name],
[name]
New York, NY
10016

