The PI will confirm prior to enrollment that each subject qualifies for the study. The eligible subject will be approached by the research team. All patients willing to participate will personally sign and date the latest IRB approved version of the consent form. Written and verbal versions of the participant information and informed consent will be presented to the participants detailing no less than: the exact nature of the study; the implications and constraints of the protocol; the known side effects and any risks involved in taking part. It will be clearly stated that the participant is free to withdraw from the study at any time for any reason without prejudice to future care, and with no obligation to give the reason for withdrawal. The participant will be allowed as much time as wished to consider the information, and the opportunity to question the Investigator, their general practitioner or other independent parties to decide whether they will participate in the study. Written Informed Consent will then be obtained by means of participant dated signature and dated signature of the person who presented and obtained the informed consent. A copy of the signed Informed Consent will be given to the participants. The original signed form will be retained at the study site, in a research binder maintained by the study team in a locked cabinet. All documents will be stored safely in confidential conditions. On all physical and electronic study-specific documents, other than the signed consent, the participant will be referred to by a study participant number/code, not by name.

Visit 2 (Day of EP procedure)

- Ensure the subject has no additional questions regarding the study
- Once the subject has been prepped for surgery, apply the sensor to the subject's upper chest using the toSense approved electrodes
- Connect the device to the power source
- Study participant will be assigned a study number/code

- All data transmitted by the CoVa2 device will be de-identified.
- Run several test measurements on the sensor to ensure that the device is actively measuring on the subject
- Explain to the subject that the sensor will measure for a 90 seconds period, with 120 second pause in between measurements
- Measurements will not be made while the subject is transferred to and from the surgery room
- Measurements will be made until the patient is discharged

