- Immediately prior to discharge, a study team member will remove the CoVa™ 2 device from the patient, and ensure a final data transmission.

Withdrawal/Early Termination Visit

If the subject withdraws from the study:

- A reasonable attempt should be made to find out why the subject dropped out of the study
- Subjects may be replaced in the study
- Record the whether the withdrawal was from either the subject or principle investigator

Ethics/Protection of Human Subjects

Ethical Standard

The investigator will ensure that this study is conducted in full conformity with Regulations for the Protection of Human Subjects of Research codified in 45 CFR Part 46, 21 CFR Part 50, 21 CFR Part 56, and/or the ICH E6.

Institutional Review Board

The protocol, informed consent form(s), recruitment materials, and all participant materials will be submitted to the IRB for review and approval. Approval of both the protocol and the consent form must be obtained before any participant is enrolled. Any amendment to the protocol will require review and approval by the IRB before the changes are implemented to the study. All changes to the consent form will be IRB approved; a determination will be made regarding whether previously consented participants need to be re-consented.

Informed Consent Process

Consent/Accent and Other Informational Documents Provided to Participants

Consent forms describing in detail the study procedures, and risks are given to the participant and written documentation of informed consent is required prior to starting intervention/administering study product. The following consent materials are submitted with this protocol:

- Informed Consent Form

Consent Procedures and Documentation

Informed consent is a process that is initiated prior to the individual's agreeing to participate in the study and continues throughout the individual's study participation. Extensive discussion of risks and possible benefits of participation will be provided to the participants and their families. Consent forms will be IRB-approved and the participant will be asked to read and review the document. The investigator will explain the research study to the participant and answer any questions that may arise. All participants will receive a verbal explanation in terms suited to their

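### Exclusion 3 screens for up to 14 hours of sensor wear, while the protocol plans about 24 hours of continuous wear after the procedure alone

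*Protocol*

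**What the plan says.** The eligibility threshold is item 3 of the Exclusion Criteria, which rules out "Subjects who are unwilling or unable to wear the sensor (and electrodes) for a period of up to 14 hours".

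The planned wear appears in several other places:

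- Description of Study Design, on the stay after the procedure: "The patient will continuously wear the CoVa™ 2 system until they are discharged for a period of about 24 hours". The same section has the sensor put on again after transfer: "Once the subject is situated in the hospital room, the CoVa™ 2 Sensor will be applied to the subject".
- Duration of Study Participation, before the procedure: "Measurement prior to EP Procedure: 1-3 hours".
- Duration of Study Participation, after the procedure: "Patient will be measured until they are discharged from hospital (approximately 24 hours").
- Visit 2 (Day of EP procedure), with no number of hours: "Measurements will be made until the patient is discharged".
- Protocol Summary, Participant Duration: "Up to 7 days (until hospital discharge").

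Nothing else in the protocol refers to 14 hours or explains the figure.

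**The concern.** An exclusion criterion on tolerance of the device should screen for the wear that the schedule asks for. Here it screens for much less. A candidate who says that 14 hours is the most they can manage is not excluded by item 3, although the schedule needs about 10 hours more after the procedure alone.

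Two things depend on it. First, the sensor data from the hospital stay are to be analysed retrospectively, and the primary endpoint is a retrospective judgement on early discharge in about 20 subjects. A subject who stops early loses the hours nearest to actual discharge. That these hours bear on the endpoint is a reasonable inference; the protocol does not say so. Second, the criterion stays in force after enrolment. Reasons for Withdrawal or Termination lets an investigator end participation when an exclusion criterion develops or comes to light later, so a wrong wear period also enters those decisions.

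Eligibility and the wear schedule are protocol content, so this is not a matter that a separate statistical analysis plan would settle.

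**Working it through.** **Inputs**

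- Wear screened for: up to 14 h (Exclusion Criteria, item 3).
- Wear after the procedure: about 24 h (Description of Study Design; Duration of Study Participation).
- Measurement before the procedure: 1 to 3 h (Duration of Study Participation); about 2 h in the Description of Study Design.
- Procedure time: measured as well, but no length is stated.
- Duty cycle: 90 s measuring, then 120 s transfer, so 90 + 120 = 210 s per cycle (Description of Study Design; Visit 2).

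**Can 14 h be reproduced from the schedule?**

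1. *Limit per application.* The sensor is applied again after the procedure, so 14 h might be a limit for one wear period. The post-procedure period alone is about 24 h and is described as continuous. Shortfall: 24 − 14 = 10 h. Coverage: 14/24 = 58%.
2. *Limit in total.* Before plus after: 1 + 24 = 25 h to 3 + 24 = 27 h, without procedure time. Shortfall: 11 to 13 h. Coverage: 14/27 = 52% to 14/25 = 56%.
3. *The 24 h read as the whole wear period.* The shortfall is still 10 h.
4. *Active measuring time only.* Over 24 h this is 24 × 90/210 = 10.3 h. Over 25 to 27 h it is 10.7 to 11.6 h. Reaching 14 h of active time would take 14 × 210/90 = 32.7 h of wear, which implies 32.7 − 27 = 5.7 h to 32.7 − 25 = 7.7 h of procedure. The protocol states no such length, and the criterion concerns wearing, not measuring.

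**Could a device limit explain 14 h?** No. The device description allows use over several hours or days, and the Product Storage and Stability table gives the electrodes 24 hours in operation.

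**Outer bound.** The Protocol Summary's limit is 7 × 24 = 168 h. It bounds participation and is not planned wear, so it does not enter the comparison.

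**What one affected subject would lose (illustration, not an expected loss).** A 24 h period holds 86,400/210 = 411 cycles and 14 h holds 50,400/210 = 240. If all 14 h fell after the procedure, 240 of 411 planned cycles would be recorded, which is the same 58%.

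**The case against.** The mismatch is hard to dispute; its consequence is not. The protocol has no run-in or wear test that would identify a subject who tolerates 14 hours but not 24. The wear problems it names are skin irritation and adhesive sensitivity, with no 14-hour cut-off for either. Under Enrollment/Baseline, consent must explain what the study demands, so someone unwilling to wear the sensor until discharge can decline then. Item 4 of the Exclusion Criteria lets the investigator exclude subjects who are medically unsuitable. No minimum wear defines an evaluable subject, 20 to 30 participants are to be recruited for 20 evaluable ones, and the Withdrawal/Early Termination Visit section adds "Subjects may be replaced in the study". The 25 to 27 hour total is also only one reading, because Visit 2 first applies the sensor once the subject is prepped for surgery, which fits poorly with 1 to 3 hours of earlier measurement.

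Most of this stands as a limit on the size of the effect. The number admitted in error is probably small, and no effect on the trial's conclusions is demonstrated. The firm comparison is 14 hours against about 24; the larger total is secondary. None of it corrects the threshold. Item 4 covers medical unsuitability, not unwillingness. Consent and replacement make up for a wrong criterion without making it right.

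**Conclusion.** The concern holds. The wear period in exclusion 3 contradicts the planned wear: it covers 58% of the post-procedure period and falls about 10 hours short, too large a gap for words such as *about* or *approximately* to absorb. With the pre-procedure period included, coverage is 52% to 56%.

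This rests on taking the 24 hours as the protocol gives them and on reading the criterion as being about wear, as it says. The mismatch itself is certain. The number of affected subjects, and whether they would count as non-evaluable, cannot be derived from the document. It should be corrected because it is an operative eligibility threshold, but it does not by itself threaten the trial.

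**What to change.** Reconcile item 3 of the Exclusion Criteria with the Participant Duration row of the Protocol Summary, the Description of Study Design and the Duration of Study Participation, so that the criterion and the planned wear state the same period. Say whether that period applies to each application of the sensor or to total wear, and whether procedure time counts. The document does not show which figure was intended, so the investigator has to settle it.

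The cost is protocol wording only. If the longer period stands, a few candidates who would accept only 14 hours become ineligible.

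### Recruitment stops at about 20 enrolled although 20 evaluable are wanted, and replacement of withdrawals is tied to the success criteria

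*Protocol*

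**What the plan says.** Four places in the Protocol bear on the count.

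- **Total Number of Participants and Sites** sets the stop: "Recruitment will end when approximately 20 participants are enrolled". The next sentence gives the yield: "It is expected that approximately 20-30 participants will be recruited in order to produce 20 evaluable participants".
- **Protocol Summary**, row Number of participants, gives "20 subjects across one site". The Brief Summary and Population rows also give about 20. None says whether these are enrolled or evaluable.
- **Handling of Participant Withdrawals or Termination** has the investigator decide on replacement. The investigator "will review whether a withdrawal of a subject affects the success criteria of the study", and then: "A subject may be replaced if it is determined that more subjects are needed based on this criterion". The section on the withdrawal visit also allows replacement, with no criterion attached.
- **Primary Study Endpoints** sets the success rule over a differently named group: "at least 50% of subjects studied in this trial are able to be discharged relatively early from the hospital".

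The Protocol uses *enrolled*, *recruited*, *evaluable* and *studied* without defining them or relating them to each other.

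**The concern.** There are two linked problems.

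The first is the count. A stop keyed to enrolment delivers the evaluable target only if every enrolled subject turns out evaluable. The Protocol itself foresees losses after enrolment: withdrawal at any time, termination by the investigator (including for an exclusion criterion recognised late), data too incomplete to evaluate, and possible interference from ablation or cardioversion with the measurements.

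The second is how losses are made good. The stated ground for replacing a subject is the effect of the withdrawal on the success criteria, and the only success criterion stated is the 50% rule. The Protocol Summary says that no blinding is used, and Description of Study Design has the device manufacturer's scientists processing data while the study runs. Who enters the sample, and so who is counted in the proportion, could then be decided by someone who knows how the proportion stands.

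In a single-arm study of about 20 subjects judged on one proportion, a few subjects either way can matter.

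**Working it through.** **Inputs.** From the Protocol: a stop at about 20 enrolled; 20 evaluable wanted; about 20-30 recruited expected; success at 50% or more. The Protocol gives no non-evaluable rate, so the rates *d* below are assumptions. It also gives no power, significance level or reference rate, so the 20 itself cannot be re-derived. Only the attrition arithmetic can be checked.

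**Step 1: reproduce the 20-30 range.** The number needed for 20 evaluable is 20 / (1 − d).
- d = 0: 20 / 1 = 20.
- d = 1/3: 20 / (2/3) = 30.

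The range therefore corresponds to 0 to 33% non-evaluable, if *recruited* and *enrolled* mean the same.

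**Step 2: what a stop at 20 enrolled delivers with no replacement.** Expected evaluable is 20 × (1 − d). The chance that all 20 are evaluable is (1 − d)^20, assuming independent losses.

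| Assumed d | Expected evaluable from 20 enrolled | Chance all 20 evaluable | Enrolled needed for 20 evaluable on average |
|---|---|---|---|
| 5% | 20 × 0.95 = 19 | 0.95^20 = 36% | 20 / 0.95 = 21.1, so 22 |
| 10% | 20 × 0.90 = 18 | 0.90^20 = 12% | 20 / 0.90 = 22.2, so 23 |
| 20% | 20 × 0.80 = 16 | 0.80^20 = 1.2% | 20 / 0.80 = 25 |

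The last column lies inside the Protocol's own 20-30. A stop at about 20 enrolled matches it only when d is at or near zero.

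**Step 3: does replacement close the gap?** Both replacement passages are permissive and both concern withdrawals. A subject who completes the study with unusable recordings is not a withdrawal, and no passage provides for replacing that subject.

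**Step 4: what tying replacement to the criterion can do.** As an illustration, suppose 20 are enrolled, one withdraws, and the withdrawn subject is left out of the proportion (the Protocol does not say whether that is so).
- With 19 subjects, half is 9.5, so 10 successes are needed. With a replacement there are 20 subjects, half is 10, and again 10 are needed.
- With 9 successes among 19 (47.4%) the criterion is missed. A replacement who succeeds gives 10/20 = 50%, and it is met. One who does not gives 9/20 = 45%, and nothing has been lost.

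Replacing when the count is one short is thus a free extra chance. A replacement rule that does not look at results removes it.

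**The case against.** The other side has good points.

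- **Two rival stopping rules?** A reader might infer that the Protocol states two. It does not: only the first sentence is a rule, and the second is an expectation. Elsewhere the Protocol speaks of approaching patients for enrolment and of confirming eligibility before it, so recruiting 20-30 to enrol about 20 is a plausible reading. What survives is that the sentence ties the 20-30 to *evaluable*, not enrolled, participants, and that no margin remains for loss after enrolment.
- **A collapse to about 13 evaluable?** Applying the extreme 1/3 loss to 20 enrolled gives 20 × 2/3 = 13.3. That takes the outer edge of a planning range, allows no replacement and ignores the word *approximately*. It is not a fair expectation.
- **A pass turning into a fail?** A reader might set 10 of 20 evaluable (50%) against 10 of 30 enrolled (33%). That needs 30 enrolled, which the stop at about 20 prevents.
- **Replacement driven by results?** The clause can also be read as asking whether enough subjects remain to judge the criterion, and the endpoint itself is to be determined retrospectively. The documents do not establish that replacement will follow results. They permit it, and the wording should not.
- **Analysis set.** Defining *evaluable* and the analysis population is commonly left to a statistical analysis plan, which was not available here. Its absence from the Protocol is not a fault. The mismatch of counts and the replacement clause are in the Protocol itself, and the clause governs conduct, which an analysis plan would not undo.

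**Conclusion.** The point holds in a limited form. The recruitment stop does not assure the 20 evaluable participants that the same section names. Under assumed losses of 5 to 20% and no replacement, the expected shortfall is about 1 to 4 subjects (19 down to 16 evaluable). Optional replacement of withdrawals would reduce this but does not reach subjects with unusable data.

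Separately, the replacement clause read literally lets the sample and the denominator of the 50% criterion depend on results. That is a possibility left open by the wording, not a stated intention.

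Severity is minor to moderate. The study is small and introductory, and no power statement is undermined. Still, its one success criterion is a bare proportion in about 20 subjects.

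**What to change.** 1. **One stopping rule.** State that recruitment ends when 20 evaluable participants are reached, within the approximately 30 already foreseen. Alternatively, restate the size as about 20 enrolled and accept fewer evaluable. Bring the 20 subjects in the Protocol Summary into line with whichever is chosen.
2. **Replacement independent of outcome.** Replace withdrawn or non-evaluable subjects by a rule fixed in advance that refers neither to the success criteria nor to any result.
3. **One denominator term.** Use a single term in the 50% criterion. Report the proportion over all subjects to whom the sensor was applied, alongside the evaluable-only figure.

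**Cost.** The changes are to wording, but the Protocol requires IRB approval of any amendment. A few more subjects may be enrolled than a stop at 20 would bring: 2 to 5 more at the assumed 5 to 20% loss (22 − 20 to 25 − 20). The all-subjects proportion may be less favourable than the evaluable-only one.

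### Subjects stopped after the sensor is on, for reasons tied to the outcome, may be replaced and left out of the 50% criterion, because no rule keeps them in the denominator

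*Protocol*

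**What the plan says.** Under Reasons for Withdrawal or Termination, an investigator may end participation on two grounds. One is an adverse event, laboratory abnormality or other medical condition that makes continuing against the subject's interest. The other is: "The participant meets an exclusion criterion (either newly developed or not previously recognized) that precludes further study participation". Subjects may also withdraw whenever they wish.

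Two of the four Exclusion Criteria matter here:
- Criterion 3: "Subjects who are unwilling or unable to wear the sensor (and electrodes) for a period of up to 14 hours".
- Criterion 4: "Subjects who are considered by the principle investigator to be medically unsuitable for study participation".

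Under Handling of Participant Withdrawals or Termination, "The Principle Investigator will review whether a withdrawal of a subject affects the success criteria of the study", and replacement may follow from that review. The Withdrawal/Early Termination Visit section adds, without a condition, "Subjects may be replaced in the study".

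Total Number of Participants and Sites says both "Recruitment will end when approximately 20 participants are enrolled" and "It is expected that approximately 20-30 participants will be recruited in order to produce 20 evaluable participants". Primary Study Endpoints sets the test: "The primary endpoint will be if at least 50% of subjects studied in this trial are able to be discharged relatively early". The protocol defines neither an evaluable participant nor a subject studied.

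**The concern.** An exclusion that was present at entry but overlooked is an eligibility matter. One that develops after the sensor is on is a post-enrolment event, and for criteria 3 and 4 that event bears on what the trial measures. A subject who cannot keep the sensor on is one in whom the device did not measure successfully, which is part of the Primary Objective. A subject judged medically unsuitable after the procedure may well have had a complication. Showing complications is also part of that objective, and a complication is a plausible reason for not going home early.

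If such subjects are treated as non-evaluable and replaced, the subjects who remain are selected towards success. The success rule is a simple proportion in about 20 subjects, so one or two removals can decide it. The principal investigator reviews withdrawals against the success criteria, and criterion 4 has no objective definition, so the removal can depend on judgement.

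**Working it through.** **The plan's own figure.** The protocol gives no alpha, power or effect size, so there is no derivation of 20 to reproduce. The recruitment range can be turned into an implied loss: 1 - 20/20 = 0% to 1 - 20/30 = 33.3%. The protocol therefore foresees that up to 10 of 30 recruits may not count.

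**Counting without replacement.** If enrolment stops at about 20 and nobody is replaced:
- 9/20 = 45.0%, criterion not met. With two of the 11 failures dropped, 9/18 = 50.0%, met.
- 8/20 = 40.0%, not met. With four of the 12 failures dropped, 8/16 = 50.0%, met.

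**Counting with replacement up to 20 evaluable.** Ten successes among 20 evaluable subjects meet the rule. With all recruits in the denominator and those lost counted as failures, the same ten give:
- 10/22 = 45.5%
- 10/25 = 40.0%
- 10/30 = 33.3%

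None of these meets it. The successes needed would be 11, 13 and 15.

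**Chance of meeting the rule.** Let p be the true success rate among all subjects on whom the sensor is applied, and f the fraction of failures removed and replaced. The rate among counted subjects is

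p' = p / [p + (1 - p)(1 - f)]

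and the criterion is met with probability P(X ≥ 10), X ~ Binomial(20, p'). At p = 0.45:
- f = 0: p' = 0.450, probability 40.9%
- f = 0.10: p' = 0.45/0.945 = 0.476, probability 50.3%
- f = 0.20: p' = 0.45/0.890 = 0.506, probability 60.8%
- f = 0.30: p' = 0.45/0.835 = 0.539, probability 71.8%

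The documents give neither p nor f, so a range is needed:

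| Assumed p | f = 0 | f = 0.10 | f = 0.20 | f = 0.30 |
|---|---|---|---|---|
| 0.40 | 24% | 32% | 42% | 54% |
| 0.45 | 41% | 50% | 61% | 72% |
| 0.50 | 59% | 68% | 77% | 85% |

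**Is this feasible within the recruitment range?** The expected number of recruits needed for 20 counted subjects is 20 / [1 - (1 - p)f]. At p = 0.45 and f = 0.20 this is 20/0.89 = 22.5. At f = 0.30 it is 20/0.835 = 24.0. Both lie within 20-30.

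**The case against.** The strongest objection is that the clause governs participation and says nothing about analysis. Where the protocol wants subjects out of the analysis it says so, as it does under Vulnerable Subjects. A subject who wore the sensor and was recorded is, on a plain reading, a subject studied, and an analysis plan that is not shown may count such subjects as failures. This stands as far as it goes. A reader might infer that the protocol directs investigators to discard failures as ineligible, and the text does not support that. Removal from the count is an inference from the evaluable target combined with replacement. However, the protocol itself fixes both of those, and an analysis plan could not recover discharge or complication data that were not collected after termination.

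It is also true that this clause is not the only route. The adverse-event ground covers a post-procedure complication without criterion 4, and a subject tired of the sensor can simply withdraw. Confining criteria 3 and 4 to the period before sensor application would therefore leave the gap open. The remedy belongs in the denominator.

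A reader might further infer that the usability objective is biased. The Secondary Objectives ask about usability for clinicians, so patient intolerance of the sensor does not bear on that objective.

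The link to outcome is plausible but not certain. A subject who cannot tolerate the sensor may be clinically fit to leave early, and counting that subject as a failure is a choice of estimand. Criterion 3 speaks of up to 14 hours, while Description of Study Design has the sensor worn for about 24 hours until discharge, so later intolerance may not literally meet it. Finally, the protocol asks for the reason for withdrawal and who initiated it. That makes removals traceable but does not settle how they are counted.

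**Conclusion.** The concern holds in a limited form. The stated rules permit removal related to outcome from a 50% criterion on about 20 subjects, by several routes, and no rule separates stopping participation from leaving the count. Stopping participation is not itself a fault.

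Two dropped failures are enough to turn 45% into 50%. With replacement, an assumed true rate of 45% and 10% to 30% of failures removed, the chance of success rises by about 9 to 31 percentage points (from 40.9% to between 50.3% and 71.8%). These figures assume that only failures are removed, that subjects are independent, and that removed subjects are replaced from the same population. They show how large the bias could be, not how large it is expected to be.

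**What to change.** Leave the grounds for stopping participation unchanged. In Primary Study Endpoints, Handling of Participant Withdrawals or Termination, and Withdrawal/Early Termination Visit, state that:
- Every subject on whom the sensor was applied stays in the primary denominator, whatever the reason for stopping, and is not replaced for the primary analysis.
- Such a subject counts as not shown to be dischargeable early, with a sensitivity analysis that excludes these subjects, and as a measurement failure for the periods not recorded.
- Discharge time and complications are taken from the hospital record where the subject's authorization allows.
- Only subjects ineligible on facts dating from before sensor application may be set aside, and they are reported separately.

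Define evaluable participant and subjects studied to match. The 14-hour wear in exclusion 3 and the roughly 24-hour wear in Description of Study Design must be reconciled.

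The cost is a short amendment and no added visits, since the data are in the hospital record. The reported success rate may be lower.
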